7 CRITERIA OF EVALUATION

Evaluable for toxicity

All patients will be evaluable for toxicity from the time of their initiated treatment with atorvastatin (T1) and until discontinued treatment (T5).

Evaluable for response

All eligible patients will be included in the response rate calculation. The subset that will be assigned a response category (see definitions below) are all patients who have received two years of minimum 80% of full dosage atorvastatin.

Response and Evaluation Endpoints

- Response according to primary endpoint:
- Atorvastatin response according to invasive disease-free-survival (IDFS) will be assigned significant in case of a significant improved IDFS. Recurrences cover all invasive recurrences.
- Response according to secondary endpoints:
- Clinical survival endpoints will be evaluated by follow-up within the trial and annual linkage to the national death registry.

All statistical analyses will be performed for the entire study population as well as in exploratory analyses separately as stated in section 2.3 order to detect a potential differentiated effect of atorvastatin depending on the clinical setting.

- Translational endpoints are described in section 10.
- Patients reported outcome are evaluated and related to differences between treatment arms in incidence of recorded symptoms.

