- Reduced performance status (ECOG>2) will require permanent discontinuation of STUDY MEDICATION.

DURATION OF THERAPY

All patients will receive STUDY MEDICATION (atorvastatin or placebo) for two years.

STUDY MEDICATION will be discontinued if:

- 1. There are any SAFETY concerns.
- 2. Cholesterol-lowering therapy becomes clinically indicated.
- 3. Discontinuation is requested by the participant and/or her treating physician.
- 4. In case of an incident breast cancer event (any invasive breast cancer, including local/regional, contralateral or distant recurrence).

Atorvastatin is a well-documented drug prescribed for continuous use over several years and the appearance of other illnesses would not indicate discontinuation of atorvastatin.

CONCOMITANT THERAPY

During STUDY MEDICATION concomitant drugs are permitted. Caution should be taken in case of:

- Digoxin treated patients should be monitored as coadministration of atorvastatin and digoxin has been shown to increase steady-state plasma digoxin concentrations by approximately 20%. Among digoxin-treated patients, plasma digoxin will be measured at baseline, after 1 week and after 1 month on STUDY MEDICATION and an increase of ≥ 20% at consequently will lead to a reduction in dosage of digoxin.
- 2. Daily intake of grapefruit juice should be avoided during atorvastatin therapy due to the grape fruit induced inhibition of CYP450 system by which atorvastatin is metabolized.
- 3. CYP3A4 inhibitors such as macrolide antibiotics (erythromycin), immunosuppressants (cyclosporine), azole antifungal agents (*i.e.*, itraconazole, ketoconazole), and some antidepressants (*i.e.*, nefazodone) should if possible be avoided during atorvastatin therapy as they may have a potential of increasing plasma concentrations of atorvastatin.

PROCEDURES (Summary)

During STUDY MEDICATION, patients will be assessed for safety and efficacy (see Schedule of Assessments tables).

Patients will receive STUDY MEDICATION for a total of two years (104 weeks).

ASSESSMENTS

EFFICACY

IDFS, defined as the time from randomization until the date of the first occurrence of one of the following events:

- Ipsilateral invasive breast tumor recurrence: invasive breast cancer involving the same breast parenchyma as the original primary.
- Regional invasive breast cancer recurrence: Invasive breast cancer in the axilla, regional lymph nodes, chest wall, and skin of the ipsilateral breast.

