- Distant recurrence: Metastatic disease-breast cancer that has either been biopsy confirmed or clinically diagnosed as recurrent invasive breast cancer.
- Death attributable to any cause, including breast cancer, nonbreast cancer, or unknown cause.
- Contralateral invasive breast cancer.
 - Second primary non-breast invasive cancer.

SAFETY

Any adverse events (AE's) will be recorded according to clinical routine during active treatment and their frequencies reported. Toxic effects will be categorized using a modified version of the NCI Common Terminology Criteria for Adverse Events, Version 5.0.

STATISTICAL ANALYSES

PRIMARY EFFICACY ENDPOINT

The primary efficacy variable is IDFS and is defined as the time between randomization and date of first occurrence of an IDFS event (as defined above in efficacy assessments).

The intention-to-treat (ITT) population will be used in the primary analysis.

The stratified log-rank test will be used to compare IDFS between the two treatment arms.

SECONDARY EFFICACY ENDPOINTS

Pathological response (neo-adjuvant patients only)

Recurrence-Free Interval

Distant Recurrence-Free Interval including associations with first site of recurrence

Overall Survival

Death attributable to any cause, including non-breast cancer or unknown cause, is considered a competing event.

Cardiac death-free interval. Cardiac death is defined as:

- Definitive cardiac death due to heart failure, myocardial infarction or documented primary arrhythmia.
- Probable cardiac death defined as sudden, unexpected death within 24 hours of a definite or probable cardiac event (e.g., syncope, cardiac arrest, chest pain, infarction, arrhythmia) without documented etiology.

Overall safety

Patient Reported Outcome

Translational biomarker endpoints (stated below)

SAFETY ANALYSES

Randomized patients who receive any amount of STUDY MEDICATION will be included in the safety analyses. Safety will be summarized by the amount of treatment actually received.

SAMPLE SIZE

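### Section 7 ties the response category, with IDFS listed under it, to two years of at least 80% of atorvastatin, which contradicts the ITT primary analysis

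*Protocol*

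**What the plan says.** Section 7, under the heading on evaluability for response, makes two statements in sequence. The first is inclusive: "All eligible patients will be included in the response rate calculation". The second narrows it. A response category, defined in the list that follows, goes to a subset only, and its members "are all patients who have received two years of minimum 80% of full dosage atorvastatin". The definitions that follow open with response on the primary endpoint: "Atorvastatin response according to invasive disease-free-survival (IDFS) will be assigned significant in case of a significant improved IDFS".

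Other parts of the protocol point the other way:

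- Trial Synopsis, primary efficacy endpoint: "The intention-to-treat (ITT) population will be used in the primary analysis", with a stratified log-rank test.
- Section 7, a few lines below the restriction: "All statistical analyses will be performed for the entire study population as well as in exploratory analyses separately". Section 2.3 says the same of the clinical endpoints.
- Section 2.3 and the synopsis time IDFS from randomization.
- Section 8.1.1 states the null hypothesis as a comparison of the randomized groups.

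Section 8.2, which describes the Kaplan-Meier, log-rank and Cox analyses, names no analysis population.

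The synopsis (duration of therapy) also lists, among the reasons to stop study medication: "In case of an incident breast cancer event (any invasive breast cancer, including local/regional, contralateral or distant recurrence").

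**The concern.** The cross-reference to the definitions below links a completers-only rule to the primary endpoint. Section 7 is the only body text that says who is evaluable for efficacy, so someone working from the body of the protocol could reasonably take it as the efficacy population.

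Used that way, the rule would do two kinds of damage. It would select patients on something that happens after randomization, namely taking at least 80% of dose for two years. It would also depend on the outcome: a patient who dies within two years, or who stops drug because of a breast cancer event, cannot qualify, although her IDFS clock began at randomization. Those early events would be lost. The rule also names only atorvastatin. If it were applied to that arm alone, atorvastatin patients would be given a period nearly free of breast cancer events and deaths that placebo patients are not given, and the comparison would be biased towards atorvastatin.

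**Working it through.** **1. Inputs (Section 8.1.1).** HR 0.75; two-sided alpha 0.05; power 80%; 379 events; annual hazard 0.0223, taken as the control arm; annual dropout 0.0103; 3 years of accrual plus 5 further years; N = 3,360, allocated 1:1 (1,680 per arm). Constant hazards and uniform accrual are assumed.

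**2. The plan's own figures.** Schoenfeld: events = 4(1.960 + 0.842)² / (ln 0.75)² = 379.35, against 379 stated. By the same formula, 379 events give 79.96% power.

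With event hazard λ, dropout δ and s = λ + δ, the probability of an observed event within follow-up u is (λ/s)(1 − e^(−su)). Averaged over u uniform on 5 to 8 years:

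- Placebo, λ = 0.0223: probability 0.1304, × 1,680 = 219.1 events.
- Atorvastatin, λ = 0.75 × 0.0223 = 0.016725: probability 0.0996, × 1,680 = 167.3 events.
- Total 386.3. For 379 events the same model needs N = 3,296, within 2% of 3,360.

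The stated sample size therefore reproduces, and it belongs to a comparison of all randomized patients.

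**3. Events in the first two years (u = 2).**

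- Placebo: (0.0223/0.0326)(1 − e^(−0.0652)) = 0.0432, × 1,680 = 72.5.
- Atorvastatin: (0.016725/0.027025)(1 − e^(−0.05405)) = 0.0326, × 1,680 = 54.7.
- Total 127.2, which is 127.2/386.3 = 33% of expected events.

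**4. Power if the rule were applied to both arms.** Power = Φ(½√d · |ln 0.75| − 1.960).

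| Setting | Events d | Power |
|---|---|---|
| All randomized, as stated | 379 | 80% |
| All randomized, expected at N = 3,360 | 386 | 81% |
| Early events dropped | 386.3 − 127.2 = 259.1 | 64% |
| Also 90% reach 80% of dose (assumed) | 233.2 | 59% |
| Also 80% (assumed) | 207.3 | 54% |
| Also 70% (assumed) | 181.4 | 49% |

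The protocol gives no adherence figure, so the last three rows are a range and not an estimate.

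**5. Why 127 is an upper bound.** It treats every early IDFS event as excluded. IDFS also counts second primary non-breast invasive cancer, and the synopsis stopping rule covers breast cancer events only. It adds that other illnesses are not a reason to stop. A patient with such a cancer in year 1 could complete two years and stay in the subset with her event. The protocol does not give the share of these cancers. If they were 10%, 20% or 30% of early events (assumed), the loss would be 114.5, 101.8 or 89.1 events, that is 30%, 26% or 23% of 386.3. Power with full adherence would then be 66%, 68% or 70%.

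**The case against.** The strongest reply is that the primary population is already settled. The synopsis says ITT, Sections 2.3 and 7 say the entire study population, and the null hypothesis compares randomized groups. The restriction governs a per-patient response category, whereas the IDFS item beneath it is a verdict on the whole trial ("will be assigned significant in case of a significant improved IDFS"). No patient-level categories follow at all, so the sentence may simply be left over from a tumour-response trial. Much of this stands: no sentence sends the log-rank or Cox analysis to this subset.

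Three stronger readings are tempting, and the documents do not support them.

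- *The primary test is biased.* A reader might infer this from the cross-reference, but the synopsis names ITT for that test.
- *Placebo patients can never qualify.* That is the literal wording, but the same section says that all patients are evaluable for toxicity from the start of atorvastatin, so it uses the drug name loosely for study medication. Simulating atorvastatin patients event-free at two years against the whole placebo arm turns a true HR of 1.00 into about 0.66 to 0.68. The protocol nowhere describes that comparison, and the simulation excludes every early IDFS event. It shows the direction of bias under a literal reading, not a property of this plan.
- *Everyone in the subset is event-free for two years by definition.* Second primary non-breast cancers make this untrue.

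Basing the calculation on eligible patients instead of randomized patients is a minor point, because Section 8.1.2 makes recorded eligibility a condition of randomization.

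The reply does not remove the contradiction. Details of adherence populations can be left to a statistical analysis plan, but here the protocol itself states a rule, links it to the primary endpoint, and says something else elsewhere.

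**Conclusion.** The point holds as an internal contradiction about who counts for efficacy, including on the primary endpoint. It does not show that the primary analysis will be biased. Under ITT nothing changes, and the 379 events and 3,360 patients stand.

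If Section 7 were followed for efficacy in both arms, up to about 127 of 386 expected events (33%) would be lost. Power would fall from 80% to about 64%, or about 54% with an assumed 80% adherence. If only the atorvastatin arm were restricted, the bias would favour atorvastatin. These figures rest on constant hazards, on 0.0223 being the control-arm hazard, on a true HR of 0.75, and on all early IDFS events being excluded, which makes the event loss an upper bound. The exclusion of breast cancer events also relies on the synopsis stopping rule, which Sections 5.1.4 and 5.1.5 do not repeat; those passages need to be reconciled.

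**What to change.** Delete the sentence in Section 7 that defines the response-category subset. State in Sections 7 and 8.2 that efficacy endpoints are analysed in all randomized patients by assigned arm, that time-to-event endpoints are timed from randomization, and that pathological response is analysed in all randomized neoadjuvant patients. This brings the body of the protocol into line with the synopsis.

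If an adherence analysis is wanted, label it supplementary, define it by study medication in both arms, and use either a two-year landmark or time-dependent adherence. Neither option restores the full protection of randomization, so it should not be presented as confirmatory.

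The cost is a wording amendment. It needs no new data and no change to the sample size, and it should be made before unblinding.

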2.3 Endpoints

Primary endpoint:

Invasive disease-free survival (IDFS), defined as the time from randomization until the date of the first occurrence of one of the following events:

- Ipsilateral invasive breast tumor recurrence: invasive breast cancer involving the same breast parenchyma as the original primary.
- Regional invasive breast cancer recurrence: Invasive breast cancer in the axilla, regional lymph nodes, chest wall, and skin of the ipsilateral breast.
- Distant recurrence: Metastatic disease-breast cancer that has either been biopsy confirmed or clinically diagnosed as recurrent invasive breast cancer.
- Death attributable to any cause, including breast cancer, non-breast cancer, or unknown cause.
- Contralateral invasive breast cancer.
- Second primary non-breast invasive cancer.

Secondary endpoints:

- A. Pathological response (only neo-adjuvant treated patients)
- B. Distant-recurrence free interval defined as time from inclusion to first distant recurrence including associations with first site of recurrence.
- C. Recurrence-free interval including associations with first site of recurrence
- D. Overall survival.
- E. Overall safety.
- F. Cardiac death-free interval. Cardiac death is defined as:
 - a. Definitive cardiac death due to heart failure, myocardial infarction or documented primary arrhythmia.

- b. Probable cardiac death defined as sudden, unexpected death within 24 hours of a definite or probable cardiac event (e.g., syncope, cardiac arrest, chest pain, infarction, arrhythmia) without documented etiology.
- G. Co-morbidity incidence beyond cardiac events during follow-up including diagnoses such as diabetes mellitus.
- H. Patient reported outcome.
- I. Translational endpoints covering i.e.:
 - a. Baseline tumor- and circulating biomarkers predicting clinical response to atorvastatin
 - b. Alterations of circulating lipid-associated biomarkers (i.e. cholesterol, LDL, HDL, triglycerides, ApoA, and ApoB) and the association with clinical response to atorvastatin.
 - c. Alterations of circulating hormone biomarkers (*e.g.*, estradiol) and the association with clinical response to atorvastatin.

All statistical clinical endpoint analyses will be performed for the entire study population as well in exploratory analyses separately for:

- neoadjuvant and adjuvant treated patients in order to detect a potential differentiated effect of statin depending on the time of systemic therapy.

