- patients receiving combined systemic therapy with chemotherapy, anti-HER2 therapy, and/or endocrine therapy AND endocrine-only treated patients.
- pre- and postmenopausal patients.

As for the randomized cohort, patients included in the observational cohort will be analyzed separately in supplemental analyses according to corresponding endpoints as specified above. In additional analyses, patients enrolled in the observational cohort will be analyzed as a third treatment arm together with the two randomized arms (atorvastatin treated, and placebo treated) and constitute information on the effects of statin use as "real world data".

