6.2 Observational cohort

Patients that are not able to participate in the randomized placebo-controlled part of the trial due to prevalent cholesterol lowering therapy (statins, fibrates, ezetimibe, PCSK9 inhibitors), but otherwise fulfil in- and exclusion criteria can be included in the observational cohort. Patients can participate in the observational cohort regardless of the dose of cholesterol lowering therapy. In this cohort no randomization or medical intervention is relevant, otherwise these patients will with a few exceptions follow the study schedule in accordance with the randomized patients.

Adverse events will be registered in the Master folder in the DBCG CRF according to the schedule above. However, SAEs are not to be reported for patients in the observational cohort.

In case the patient terminates cholesterol-lowering medication for any reason, the patient is still followed according to the trial protocol. It should be registered in the CRF folder "Master End of Trial" if the patient stops medication (End of treatment) and if the patients for any reasons stops participating in this study (End of trial).

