8 STATISTICAL CONSIDERATIONS

8.1 Statistical design

8.1.1 Sample size

Design

A multi-center randomized placebo-controlled double-blind phase III trial investigating the effects of atorvastatin on breast cancer in the (neo)adjuvant setting.

Sample size

The sample size calculations are based on estimates of 10-year IDFS with an annual hazard rate of 0.0223. A sufficient number of patients is sought to provide 80% power using a two-sided 0.05-level test to detect a 25% reduction in the risk of an IDFS event (hazard ratio=0.75). A total of 379 events are required. With an estimated 5% drop-out at 5 years (annual rate 0.0103), this is estimated to be achieved by a total recruitment of 3,360 participants and a $6\frac{1}{2}$ years follow-up. The sample size estimate is based on inclusion for 3 years, a median follow-up of $6\frac{1}{2}$ year, that is 5 years of additional follow-up after the 3 years of inclusion.

Hypothesis

H0: (Neo)adjuvant atorvastatin treatment has no impact on invasive disease-free survival for breast cancer patients and survival rates do not differ between randomized groups; atorvastatin versus placebo.

Ha: Atorvastatin treatment influence invasive disease-free survival in breast cancer.

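### Separate subgroup analyses cannot detect a differential effect, and the observational third arm cannot be read as an effect of statins

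*Protocol*

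**What the plan says.** Section 2.3 of the protocol runs the clinical endpoint analyses on the whole study population and, as exploratory analyses, separately for three pairs of subgroups. The first pair is "neoadjuvant and adjuvant treated patients in order to detect a potential differentiated effect of statin depending on the time of systemic therapy". The second is "patients receiving combined systemic therapy with chemotherapy, anti-HER2 therapy, and/or endocrine therapy AND endocrine-only treated patients". The third is pre- and postmenopausal patients. Section 7 repeats the plan and its purpose: "exploratory analyses separately as stated in section 2.3 order to detect a potential differentiated effect of atorvastatin depending on the clinical setting". No interaction or other between-subgroup contrast is mentioned. Section 8.1.2 stratifies the randomization by site and by clinical setting in three levels: neoadjuvant, adjuvant early entry and adjuvant late entry.

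On the observational cohort, section 2.3 first plans separate supplemental analyses. It then states that, in additional analyses, "patients enrolled in the observational cohort will be analyzed as a third treatment arm together with the two randomized arms", as real-world information on what statin use does. Section 6.2 says who is in that cohort: patients who cannot be randomized "due to prevalent cholesterol lowering therapy (statins, fibrates, ezetimibe, PCSK9 inhibitors"), whatever the dose. Section 2.2 sets a more modest objective for them, namely to evaluate prognosis.

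**The concern.** Two stated methods do not fit their stated purposes.

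First, a differential effect is a difference between two treatment effects. Two separate tests against no effect do not estimate that difference. Each subgroup has fewer events than the trial and so lower power, and one subgroup being significant while the other is not is an ordinary result when the true effect is the same in both. The risk is a false claim that atorvastatin works in, say, adjuvant but not neoadjuvant patients. The timing question is also only half covered. Section 2.3 aims at an effect by time of systemic therapy but lists neoadjuvant against adjuvant only, although late entrants may be up to three years into endocrine therapy and section 8.2 expects them to be prominent early in accrual.

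Second, calling the observational cohort a treatment arm and reading it for effects of statin use asks too much of it. Its members need not be on a statin, they are selected by the reason for treatment and by having tolerated it, and the primary endpoint is timed from an event they do not have.

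**Working it through.** **Inputs from section 8.1.1.** Error rates: "A sufficient number of patients is sought to provide 80% power using a two-sided 0.05-level test". Target effect: a hazard ratio of 0.75. Control arm: an annual hazard of 0.0223. Also 379 events, an annual drop-out rate of 0.0103, 3,360 participants, and 3 years of inclusion plus 5 years of follow-up. Allocation is 1:1.

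**Assumption.** The documents give no event shares by subgroup, so a range of splits is shown.

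**The plan's own figures.** With D = 4(z₀.₉₇₅ + z₀.₈₀)² / (ln HR)², the required events are 4 × (1.960 + 0.842)² / 0.2877² ≈ 379.3, which matches 379. With exponential event and drop-out times, uniform accrual and 1,680 per arm at hazards 0.0223 and 0.0167, about 386 events are expected. The plan's numbers are sound.

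**Separate tests under one common effect.** For a subgroup with share f of D = 379 events, power = Φ(√(fD)/2 × 0.2877 − 1.96). The two subgroups contain different patients, so P(exactly one significant) = p₁(1 − p₂) + p₂(1 − p₁).

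| Event split | Power, smaller subgroup | Power, larger subgroup | Exactly one significant |
|---|---|---|---|
| 50:50 | 0.508 | 0.508 | 50% |
| 30:70 | 0.335 | 0.649 | 55% |
| 20:80 | 0.240 | 0.707 | 61% |
| 10:90 | 0.141 | 0.757 | 68% |

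For the 50:50 row: √189.5/2 × 0.2877 − 1.96 = 0.02, Φ(0.02) = 0.508, and 2 × 0.508 × 0.492 = 0.50. Using the expected 386 events leaves the first three percentages at 50, 55 and 61. With no effect anywhere, a pair is discordant in 2 × 0.05 × 0.95 = 9.5% of trials.

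**Interaction test.** Its false-positive rate is 5% per factor, whether or not atorvastatin works. Its power to separate HR 0.75 from HR 1.0 at 379 events split 50:50: the standard error of the difference in log hazard ratios is √(4/189.5 + 4/189.5) = 0.2055; 0.2877/0.2055 = 1.40; Φ(1.40 − 1.96) ≈ 0.29. At 10:90 it falls to about 0.13.

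**Third arm.** No bias can be calculated, because the documents give no size, drug mix or adjustment set for the cohort. The sections can be set side by side:

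- Exposure: section 2.3 speaks of statin use; sections 3.2 and 6.2 admit fibrates, ezetimibe and PCSK9 inhibitors, and section 6.2 admits any dose.
- Time origin: section 2.3 counts IDFS from randomization; section 6.2 says the cohort has none, and the procedures table in section 6.6 has a registration row instead.
- Purpose: section 2.2 says prognosis; section 2.3 says effects.

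**The case against.** The strongest reply is that little depends on this text. The subgroup analyses are called exploratory and the cohort analyses supplemental or additional. The primary comparison in the synopsis is a stratified log-rank test of the two randomized arms by intention to treat, and none of this enters it. Interaction tests and adjustment sets are commonly left to a statistical analysis plan, which is not shown. The protocol also states no rule that a differential effect is declared when one subgroup is significant and the other is not, so the 50–61% is the error rate of a reading that it does not spell out.

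Most of that stands, and it limits the weight of the point. It does not remove it: the protocol fixes both the aim (detection of a difference) and the method (separate analyses), and an exploratory label does not make the method answer the question.

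Four stronger readings are tempting, and the documents do not support them:

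- A reader might infer that spurious claims of a statin effect would follow. Under a uniform hazard ratio of 0.75 the drug works, and what is false is the heterogeneity. Bias in the third-arm comparison could run in either direction.
- A reader might infer that the therapy subgroup is formed after randomization and so could be shaped by treatment. Nothing shows the therapy class being chosen after randomization or influenced by arm. The synopsis says standard therapy follows guidelines irrespective of randomization, and the trial is double-blind.
- A reader might infer that early against late adjuvant entry will never be examined. It is not listed in section 2.3, but section 7 speaks of the clinical setting, the name section 8.1.2 gives to the three-level factor, and further exploratory subgroups are not excluded.
- A reader might infer that the third-arm analysis must be deleted. The cohort is already labelled non-randomized and also gets its own separate analysis, and section 8.2 foresees confounder-controlled Cox models. A properly labelled additional comparison is not an error in itself; dropping it would be a preference.

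**Conclusion.** The point holds as a mismatch between stated aim and stated method in secondary analyses. If discordant significance is taken as evidence of a differential effect, a uniform hazard ratio of 0.75 produces that pattern in roughly half to three-fifths of trials for each pair of subgroups, against 5% for an interaction test. These figures rest on 379 events, proportional hazards, 1:1 allocation within subgroups, and event splits between 50:50 and 20:80 that are assumed.

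The third-arm wording claims more than the cohort can give, because of mixed drug classes and doses, no randomization date, and an objective elsewhere limited to prognosis. No size can be put on this from the documents.

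The primary ITT analysis and the sample size are untouched.

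**What to change.** **Subgroups (sections 2.3 and 7).** State that differential effects are assessed by treatment-by-subgroup interaction, reported with the hazard ratio and confidence interval in each subgroup, and labelled exploratory. Replace the neoadjuvant/adjuvant split by the three-level clinical setting of section 8.1.2, so that early and late adjuvant entry are compared.

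**Observational cohort (section 2.3).** Limit any comparison with the randomized arms to statin users. Define time zero for this cohort as registration. Adjust for covariates. Describe the result as a non-randomized association, in line with the prognosis objective in section 2.2, and not as an effect of statins. The separate supplemental analysis can stay as it is.

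**Cost.** Some rewording and minor programming. The comparison of statin users needs the drug class to be known at registration; section 2.2 already foresees information on prevalent use. The drawback to state openly is low power: about 29% to separate a hazard ratio of 0.75 from 1.0 at an equal event split and less at unequal ones, so a non-significant interaction must not be reported as evidence of a uniform effect.
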